8. RESEARCH METHODS

8.1 Study type and study design

The proposed design for this study is a patient-level DUS study as “off-the-shelf”, as described in the DARWIN EU[®] Complete Catalogue of Standard Data Analyses. We will also perform a patient-level characterisation.

Table 2. Description of potential study types and related study designs.

Study type	Study design	Study classification
Patient Level DUS	New drug/s user cohort	Off the shelf

8.2 Study setting and data sources

This study will use routinely collected health data from 5 databases in the DARWIN EU[®] network of data partners from 4 European countries. All databases were previously mapped to the OMOP CDM.

Data sources

1. Clinical Practice Research Datalink (CPRD) GOLD, United Kingdom
2. Integrated Primary Care Information (IPCI), Netherlands
3. IQVIA Disease Analyzer Germany (IQVIA DA Germany), Germany
4. Institut Municipal Assistència Sanitària Information System (IMASIS), Spain
5. The Information System for Research in Primary Care (SIDIAP), Spain

These databases fulfil the criteria required for patient-level drug utilisation, and characterisation allowing for large-scale characterisation while covering different regions of Europe. The selection of databases was based on the availability of data on the selected drugs of interest, the conditions of interest, and other

	D2.2.3 - Study Protocol for P3-C1-014	
	Author(s): [name], [name]	Version: V4.0
		Dissemination level: Public

variables needed to perform the described analyses. As information needs to be provided in a timeline manner, data partners not requiring IRB approval or DPs with fast IRB review time (for instance because of basket protocol approval) have been selected. Detailed information on the selected data sources is described in [Table 3](#).

When it comes to assessing the reliability of data sources, the data partners are asked to describe their internal data quality process on the source data as part of the DARWIN EU[®] onboarding procedure. To further ensure data quality, we utilised the Achilles tool, which systematically characterises the data and generates data characteristics such as age distribution, condition prevalence per year, data density, measurement value distribution can be compared against expectations for the data. Additionally, the data quality dashboard (DQD) provides more objective checks on plausibility consistently across the data sources. In terms of relevance, more general-purpose diagnostic tools, CohortDiagnostics and DrugExposureDiagnostics, were developed. The CohortDiagnostics package provides additional insights into cohort characteristics, record counts and index event misclassification. The *DrugExposureDiagnostics* package assesses ingredient specific diagnostics for drug exposure records. Furthermore, data is maintained up to date by extracting the release dates for each dataset in the network and monitoring when data are out-of-date with the expected refresh cycle (typically quarterly or half-yearly). In addition, it is important to have clear understanding of the time covered by each released database, as this can vary across different domains. To facilitate this, the *CDMOnboarding* (and *Achilles*) packages contain a 'data density' plot. This plot displays the number of records per OMOP domain monthly. This allows us to get insights when data collection started, when new sources of data were added and when until when data was included.

	D2.2.3 - Study Protocol for P3-C1-014	
	Author(s): [name], [name]	Version: V4.0
	Dissemination level: Public	

Table 3. Description of the selected data sources.

Country	Name of Database	Justification for Inclusion	Health Care setting (e.g. primary care, specialist care, hospital care)	Type of Data (EHR, claims, registries)	Number of active subjects	Feasibility count of exposure (Azathioprine)*	Data lock for the last update
United Kingdom	CPRD GOLD	Adequate number of patients exposed to Azathioprine, availability of medical history for cohort characterisation. Able to perform study and produce results before mid-October deadline.	Primary care	EHR	17m	199,700	01/01/2024
Netherlands	IPCI	Adequate number of patients exposed to Azathioprine, availability of medical history for cohort characterisation. Able to perform study and produce results before mid-October deadline.	Primary Care	EHR	1.39m	15,700	30/04/2024
Spain	SIDIAP	Adequate number of patients exposed to Azathioprine, availability of medical history for cohort characterisation.	Primary care	EHR	5.8m	29,200	30/06/2023
Germany	IQVIA DA Germany	Adequate number of patients exposed to Azathioprine, availability of medical history for	Primary care and outpatient	EHR	43m	80,400	30/09/2023

	D2.2.3 - Study Protocol for P3-C1-014	
	Author(s): [name], [name]	Version: V4.0
	Dissemination level: Public	

Country	Name of Database	Justification for Inclusion	Health Care setting (e.g. primary care, specialist care, hospital care)	Type of Data (EHR, claims, registries)	Number of active subjects	Feasibility count of exposure (Azathioprine)*	Data lock for the last update
		cohort characterisation. Able to perform study and produce results before mid-October deadline.	secondary care				
Spain	IMASIS	Adequate number of patients exposed to Azathioprine, availability of medical history for cohort characterisation. Able to perform study and produce results before mid-October deadline.	Inpatient hospital care and secondary outpatient care	EHR	1.1m	2,100	10/02/2024

Version: V2.0 Dissemination level: Public	D2.2.3 - Study Protocol for P3-C1-014	
	Author(s): [name], [name]	Version: V4.0
		Dissemination level: Public

Clinical Practice Research Datalink GOLD, United Kingdom (University of Oxford)

The Clinical Practice Research Datalink (CPRD) GOLD is a database of anonymised electronic health records (EHR) from General Practitioner (GP) clinics in the UK that use the Vision® software system for their management.(11) The source population encompasses 98% of the UK, registered with GPs responsible for non-emergency care and referrals. Participating GPs provide CPRD EHR for all registered patients who did not specifically request to opt out of data sharing. Covering 4.6% of the current UK population, GOLD includes 4.9% of contributing GP practices, providing comprehensive information within its defined source population. GOLD contains data from all four UK constituent countries and the current regional distribution of its GP practices is 5.7% in England, 55.6% in Scotland, 28.4% in Wales, and 10.2% in Northern Ireland (May 2022).

GOLD data include patient’s demographic, biological measurements, clinical symptoms and diagnoses, referrals to specialist/hospital and their outcome, laboratory tests/results, and prescribed medications. GOLD has been assessed and found broadly representative of the UK general population in terms of age, gender, and ethnicity.(11) GOLD has been widely used internationally for observational research to produce nearly 3,000 peer-reviewed publications, making GOLD the most influential UK clinical database so far(12-14).

The Integrated Primary Care Information (IPCI), the Netherlands

The Integrated Primary Care Information (IPCI) database is a longitudinal observational database containing routinely collected data extracted from computer-based patient records of a selected group of general practitioners (GPs) across the Netherlands.(15) IPCI was started in 1992 by the department of Medical Informatics of the Erasmus University Medical Center in Rotterdam. The current database includes patient records from 2006 on, when the size of the database started to increase significantly. The demographic composition of the IPCI population mirrors that of the general Dutch population in terms of age and sex. Although the geographical spread is limited, GP practices are located in urban and non-urban areas.

Patient-level data includes demographic information, patient’s complaints and symptoms, diagnoses, laboratory test results, lifestyle factors and correspondence with secondary care, such as referral and discharge letters. For complaints, symptoms and diagnoses, Dutch GPs use International Classification of Primary Care (ICPC-1) coding, an international standard developed and updated by the World Organization of Family Doctors’ (WONCA) International Classification Committee.

IPCI data quality has been previously documented and IPCI has proved valuable for epidemiological studies.(16-20) In terms of quality control, extensive quality control steps are performed prior to each data release. These include comparison of patient characteristics between practices and checks to identify abnormal temporal data patterns in practices. Additional checks include over 200 indicators related to population characteristics (e.g. reliability of birth and mortality rates) and medical data (e.g. availability of durations of prescriptions, completeness of laboratory results, availability of hospital letters and prescriptions, proportion of patients with blood pressure measurement, etc.(15) Based on this information, two quality scores have been created. Practices with low scores have been excluded.

Information System for Research in Primary Care (SIDIAP), Spain

The Information System for Research in Primary Care (SIDIAP) is a dynamic database of pseudo-anonymized electronic health records of the primary care patient population in Catalonia, Spain.(21) (REF 16 doxy) It contains data of approximately 80% of the Catalan population registered in over 280 primary care practices throughout Catalonia since 2005.

	D2.2.3 - Study Protocol for P3-C1-014	
	Author(s): [name], [name]	Version: V4.0
	Dissemination level: Public	

The database contains data recorded in primary care centres on a daily basis. Additionally, it integrates data from external sources including biomarkers data from laboratories and records of drug prescription and dispensation. The dataset covers demographics, all-cause mortality, disease diagnoses classified under the International Classification of Diseases 10th revision (ICD-10), prescription and dispensation records of drugs, results of laboratory tests, socio-economic indicators, vaccination records, lifestyle information, parent–child linkage and various clinical parameters. Additional data from other data sources such as hospital discharges, mental health centres or specific disease registries can be obtained through diverse linkages. The demographic composition within SIDIAP closely mirrors that of the broader Catalan population, encompassing a representative spectrum of geographic distribution, age, and sex proportions. The database is updated every 6 months.

SIDIAP data quality has been previously documented and SIDIAP has proved valuable for epidemiological studies.(22-30) In terms of data integrity and reliability, SIDIAP has been subject to rigorous evaluation. Quality checks have been implemented including central identification of duplicate patient ID and visual inspection for temporal patterns in the registry of a certain variable. Furthermore, the data undergoes assessment for availability (longitudinally and reliability), plausibility (range checks and unusual values) and consistency using visualization tools. Specifically, for biochemistry data, consistency for measurements taken in different laboratories is assessed, and unit conversion is undertaken when needed.

IQVIA Disease Analyser (DA) Germany, Germany

IQVIA Disease Analyzer (DA) Germany is a database of de-identified electronic medical records from specialized and general primary practices (GP) in Germany since 1992. This dataset encompasses approximately 3% of all outpatient practices within Germany, ensuring a substantial representation of the national healthcare landscape.(31, 32) The sampling methods used for practice selection, taking into account physician’s demographics, specialty focus, community size category and federal state location, was instrumental in constructing a database that accurately mirrors the diverse spectrum of healthcare providers in the country.(31, 32) Consequently, data within IQVIA DA Germany database has been demonstrated to be representative of general and specialised practices throughout Germany.

The database contains demographics records, basic medical data, disease diagnosis according to International Classification of Diseases, 10th revision (ICD-10), and prescription records.(32) While the database partly records information on deaths and procedures, it currently does not support linkage with external data sources and therefore information on mortality is incomplete. Routine updates are conducted at regular intervals. The quality of data is assessed based on several criteria including completeness of information and correctness (e.g. linkage between diagnosis and prescriptions). IQVIA DA Germany is suitable for pharmacoepidemiologic and pharmaco-economic studies as previously demonstrated.(25, 32, 33)

The Institut Municipal Assistència Sanitària Information System (IMASIS), Spain

The Institut Municipal Assistència Sanitària Information System (IMASIS) is the Electronic Health Record (EHR) system of Parc de Salut Mar Barcelona (PSMar) which is a complete healthcare services organisation. Currently, this information system includes and shares the clinical information of two general hospitals (Hospital del Mar and Hospital de l’Esperança), one mental health care centre (Centre [name]) and one social-healthcare centre (Centre Fòrum) including emergency room settings, that are offering specific and different services in the Barcelona city area (Spain). At present, IMASIS includes clinical information from around 1 million patients with at least one diagnosis and who have used the services of this healthcare system since 1990 and from different settings such as admissions, outpatients, emergency room and major ambulatory surgery. The diagnoses are coded using The International Classification of Diseases ICD-9-CM and ICD-10-CM. The average follow-up period per patient in years is 6.37 (SD±6.82). IMASIS-2 is

	D2.2.3 - Study Protocol for P3-C1-014	
	Author(s): [name], [name]	Version: V4.0
		Dissemination level: Public

the anonymised relational database of IMASIS which is used for mapping to OMOP including additional sources of information such as the Tumours Registry.

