8.5 Study population with inclusion and exclusion criteria

The study population will include all individuals observed in one of the participating data sources during the study period (1st January 2000 to 31st December 2023) and having at least 1 year of database history.

Patients will be excluded if the start date in the database falls within 365 days prior to the index date, as sufficient data availability is required.

The operational definitions of the inclusion and exclusion criteria are presented by means of **Table 5** and **Table 6** , respectively.

	D2.2.3 - Study Protocol for P3-C1-014	
	Author(s): [name], [name]	Version: V4.0
	Dissemination level: Public	

Table 5. Operational definitions of inclusion criteria.

Criterion	Details	Order of application	Assessment window	Care Settings ¹	Code Type	Diagnosis position ²	Applied to study populations:
Prior database history	Study participants will be required to have 365 days of prior history observed before the index date	Prior	[-365,-1]	OP	N/A	N/A	All individuals within selected databases
Observation period in the database during the period	All individuals present in the 2000-2023 (or the latest date available)	after	N/A	OP	N/A	N/A	All individuals within selected databases
User of Azathioprine (exposure)	Prescription record of azathioprine	after	Study period	OP	RxNorm	N/A	All individuals within selected databases

¹ IP = inpatient, OP = outpatient, ED = emergency department, OT = other, n/a = not applicable

² Specify whether a diagnosis code is required to be in the primary position (main reason for encounter)

	D2.2.3 - Study Protocol for P3-C1-014	
	Author(s): [name], [name]	Version: V4.0
	Dissemination level: Public	

Table 6. Operational definitions of exclusion criteria.

Criterion	Details	Order of application	Assessment window	Care Settings ¹	Code Type	Diagnosis position ²	Applied to study populations:	Measurement characteristics/validation	Source for algorithm
N/A	N/A	N/A	N/A	N/A	N/A	N/A	N/A	N/A	N/A

¹ IP = inpatient, OP = outpatient, ED = emergency department, OT = other, n/a = not applicable

² Specify whether a diagnosis code is required to be in the primary position (main reason for encounter)

	D2.2.3 - Study Protocol for P3-C1-014	
	Author(s): [name], [name]	Version: V4.0
		Dissemination level: Public

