8.7 Study size

No sample size has been calculated as this is a descriptive Drug Utilisation Study where we are interested in the characteristics of all incident cases of new users of Azathioprine in each database. Based on a preliminary feasibility assessment, the expected person counts for Azathioprine were 900 for IMASIS, 6,000 for IPCI, 23,700 for IQVIA DA Germany, 24,500 for SIDIAP and 52,100 for CPRD GOLD.

The study period is from 2000-2023 but it should be noted that not all DPs do have observations period starting from 2000 on. For IPCI, observation period starts from 2008 and for SIDIAP from 2005.

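### The 365-day history rule runs from the person's general database start, so it does not guarantee a year of drug-recorded history before azathioprine use is called new

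*Protocol*

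**What the plan says.** The general text on data quality in Section 8.2 warns that "it is important to have clear understanding of the time covered by each released database, as this can vary across different domains". It names a data-density plot for this purpose: "This plot displays the number of records per OMOP domain monthly". Of its use it says: "This allows us to get insights when data collection started, when new sources of data were added". The same section mentions *DrugExposureDiagnostics* and *CohortDiagnostics*. None of these outputs is given a consequence for who enters the cohort.

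The entry rule is fixed elsewhere:

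- Section 8.5: "Patients will be excluded if the start date in the database falls within 365 days prior to the index date".
- Table 5: "Study participants will be required to have 365 days of prior history observed before the index date", with window [-365,-1] and no domain named.
- Table 4 (Section 8.4) sets the index date at the first azathioprine treatment in the study period, with a washout over any earlier time. Table 7 (Section 8.6.1) gives that washout as [-inf,-1].

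Table 3 lists a data lock for each source but no start of drug recording. Sections 8.7 and 11 give observation starts for IPCI and SIDIAP only. Section 11 does not list, as a limitation, the entry of ongoing users as new ones.

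**The concern.** A new-user design needs a stretch of time in which a prescription would have been seen had there been one. The protocol's rule secures observed time, but not time in which drugs were being recorded. If a source holds diagnoses or visits from an earlier date than prescriptions, a patient already on azathioprine can meet the history criterion on non-drug data. That patient also passes the washout, because no prescription could have been recorded, and is then indexed at the first prescription to appear.

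For such a patient, age at first prescription (objective 1) is too high by the time already on treatment. The first-era duration (objective 4, Section 8.8.1) is the remainder of a course already under way. Some may also have no indication code within -90/+30 days and so fall into the category for no listed indication (objective 2). Section 6 links portal hypertension to long-term use, so duration is central to the study's purpose. Results are reported by database without pooling (Section 8.9), so an artefact confined to one source could be read as a real difference between sources.

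**Working it through.** The plan states no figure on this point, and Section 8.7 calculates no sample size, so there is nothing to reproduce. The check has four steps.

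**1. When does an ongoing user get in?** Let observation start at day 0, drug recording at day L, and prescriptions recur every q days at random phase. The first recorded prescription falls at day L + w, with w uniform on (0, q). The washout is empty by construction, so the patient enters if L + w ≥ 365:

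share admitted = (L + q − 365)/q, held between 0 and 1.

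L and q are assumptions; the protocol gives neither.

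| L (days) | q = 28 | q = 90 | q = 180 |
|---|---|---|---|
| 180 | 0% | 0% | 0% |
| 270 | 0% | 0% | 47% |
| 300 | 0% | 28% | 64% |
| 350 | 46% | 83% | 92% |
| 365 or more | 100% | 100% | 100% |

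For example, at q = 90 and L = 300: (300 + 90 − 365)/90 = 25/90 = 28%. For regularly treated patients the existing rule works until the lag approaches a year, and fails completely from 365 days on. The drug-recording start must also lie after 01/01/2000. Otherwise the ongoing user's first recorded prescription precedes the study period and the washout removes the patient.

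**2. How large could the share be in an affected source?** Take a constant initiation rate λ, mean treatment span D years and T years of drug recording. Ongoing users when recording starts number λD, and true initiators over T years number λT, so the share wrongly included is D/(D + T):

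| D | T = 10 | T = 20 |
|---|---|---|
| 1 | 1/11 = 9.1% | 1/21 = 4.8% |
| 3 | 3/13 = 23.1% | 3/23 = 13.0% |
| 5 | 5/15 = 33.3% | 5/25 = 20.0% |

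This is an upper bound for the given D and T. It treats every ongoing user as already observed long enough to qualify, in a population of constant size. People who join after drug recording starts face no lag. D and T are assumed.

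**3. Effect on age and duration.** With a constant stopping hazard, mean elapsed time among ongoing users equals D, so their age at index is too high by 1, 3 or 5 years on average. Over the whole cohort the shift in mean age is D²/(D + T): from 1/21 = 0.05 years (D = 1, T = 20) to 25/15 = 1.67 years (D = 5, T = 10). Under that hazard the residual duration has the same distribution as a full course, so the duration summary would not move.

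With a falling hazard (Weibull, shape 0.7, mean 3 years), mean elapsed time is 3 × Γ(1 + 2/0.7)/(2Γ(1 + 1/0.7)²) = 4.71 years. The residual median is then 2.76 years, against 1.40 for true starters. The size of any distortion of duration therefore depends on an unknown hazard shape.

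**4. What the protocol shows by source.** No drug-recording start is given for any of the five. IMASIS has clinical information since 1990 from several care settings, with no statement of when prescriptions began to be recorded. It contributes 900 of the expected 900 + 6,000 + 23,700 + 24,500 + 52,100 = 107,200 persons, or 0.8%.

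**The case against.** The strongest reply is that the condition for harm is not shown to occur. Section 8.2 says coverage can vary, in a general paragraph on the network; it does not say that it differs in these sources. Databases were chosen for availability of data on the drug. CPRD GOLD and IQVIA DA Germany, with 52,100 + 23,700 = 75,800 of 107,200 expected persons (71%), list prescriptions among the contents of the practice record. Checks also exist: the density plot, *DrugExposureDiagnostics*, *CohortDiagnostics* and test runs. All of this stands, and it limits the point to an unguarded risk. It does not close the gap, because the entry rule is already fixed in Section 8.5 and Tables 4, 5 and 7, and no check is tied to it.

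Three stronger readings are tempting, and the protocol does not support them:

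- **That its dates reveal a lag.** For IPCI, "The current database includes patient records from 2006 on", while Section 8.7 says "For IPCI, observation period starts from 2008 and for SIDIAP from 2005". Records before observation is the opposite of the order required, and neither date is specific to drugs. For SIDIAP, Section 8.2 says "it integrates data from external sources including biomarkers data from laboratories and records of drug prescription and dispensation"; that describes where the data come from, not when they begin.
- **That any lag admits ongoing users.** Step 1 shows that regular users are still excluded until the lag nears a year. A shorter lag only shortens the drug look-back.
- **That ongoing users necessarily lose their indication.** Section 8.6.3 asks for a disease code in the window, not a first diagnosis. A chronic patient coded at a visit in that window is still classified.

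**Conclusion.** The point holds as a gap in the entry rule. The protocol recognises that coverage can vary by domain and has the tool to see it, but requires only 365 days from the general database start. It does not establish that any ongoing user will be misclassified in these five databases.

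The effect is zero in a source with no lag. It arises only where drug recording began about a year or more after observation and after 01/01/2000. Under the assumed D and T, the share wrongly included in such a source is then at most 5% to 33%. That range must not be read as an expected effect, for one source or for the study. Whether IMASIS or any other source meets the condition can be checked before the analysis is run. The change is worth making because it is cheap and replaces a stated rule with one less open to bias.

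**What to change.** In Table 3, add for each database the date from which drug-exposure records are consistently present. Read it from the data-density plot and state the criterion used. A plot of monthly counts shows when records appear, not that they are complete, so the criterion matters; one option is the first month from which drug records per person under observation stay level. If no date can be set for a source, say so in Section 11.

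In Section 8.5 and Table 5, require the index date to be at least 365 days after the later of that date and the person's observation start. The washout in Tables 4 and 7 can stay as written: an ongoing user's first recorded prescription then falls inside the excluded year, and the washout stops that user from being indexed later.

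The cost is one date and one cohort filter per database, using a plot the network already produces. In a source with a lag, some true early initiators are lost: at most one year of index dates, or 1/T under constant initiation (1/10 = 10% for T = 10, 1/20 = 5% for T = 20). One date per source does not capture differences between practices. Where there is no lag, nothing changes.
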